The primary goal of the proposed study is to compare TBT and matching DSTs in a large, randomized investigation in a Veteran sample via a non-inferiority design. The study will use a repeated measures RCT design to compare TBT to DSTs in 306 Veterans with PTSD, MDD, panic disorder and/or agoraphobia (PD/AG) and related symptoms of depression/anxiety and impairments. DSTs will be matched to participants' targeted diagnosis (e.g., Cognitive Processing Therapy for PTSD, CBT for MDD, and CBT for PD/AG). Assessments of disorder-specific symptomatology, as well general symptoms of the depressive/anxiety disorders and related impairments, will be used due to the transdiagnostic approach and related research aims of the proposed study. Assessments will be completed at baseline, mid-treatment, immediate post-treatment, and 6-month post-treatment follow-up. Process variables (satisfaction, attendance, discontinuation rates) also will be recorded.

Primary Aim: To examine efficacy of TBT on improving psychiatric symptomatology and related impairments in Veterans with depressive/anxiety disorders compared to DSTs.

Hypothesis: TBT will result in non-inferior improvements in psychiatric symptomatology, as assessed by the PTSD Checklist for PTSD, PHQ-9, Panic Disorder Severity Scale for PD/AG, and transdiagnostic anxiety on the State Trait Inventory for Cognitive and Somatic Anxiety and transdiagnostic impairment on the Illness Intrusiveness Rating Scale, compared to the DST control conditions.

Secondary Aim: To examine feasibility and acceptability of TBT

Hypothesis: TBT will be well tolerated by Veterans as demonstrated by improved attendance (number of weeks to complete treatment), treatment discontinuation rates (yes/no), and patient satisfaction questionnaires, as assessed by the Satisfaction with Therapy and Therapist Scale – Revised, as compared to the DSTs.

B. BACKGROUND AND SIGNIFICANCE

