
Following testing of design effects, sensitivity analyses will be conducted using the complex estimator in Mplus which can adjust the model for potential therapist effects.

Feasibility and Acceptability Analyses (Secondary Aim)

Measures of feasibility and acceptability are discontinuation proportions (discontinuation y/n), proportion of sessions attended, proportion of homework assignments completed, and patient satisfaction scores on the STTS-R. Frequency distributions describing the participants' reasons for noncompliance and discontinuation of participation will be developed. Because feasibility and acceptability analyses involve changes from baseline to post-intervention only and several of the outcomes are categorical, the generalized linear mixed model (GLMM) framework will be used to compare TBT to DST on treatment satisfaction, retention (discontinuation), and treatment adherence (% missed sessions, % homework completion). Discontinuation proportions (dichotomous outcome), % of missed visits, and % homework completion will be compared between the intervention groups using GLMM, with logistic/binomial regression analyses as special cases for dichotomous and percentage outcomes; STTS-R will be modeled as a continuous outcome using an appropriate link function. We also will model the longitudinal profile of adherence as a dichotomous outcome at each visit (e.g. attended/did not attend a given session). This will allow us to evaluate the trends in session attendance and to determine if the trends differ by treatment (e.g. whether the probability of missing visits is less/greater at earlier or later time points).

E. PROTECTION OF HUMAN SUBJECTS

RISKS TO THE SUBJECTS

Risks to the Subjects

Participants will include 306 VAMC patients in the mental health service. The inclusion criteria are that participants must: 1) be an adult (18 – 80 years in age), 2) be competent to provide informed consent for research participation, and 3) be diagnosed with MDD, PTSD, and/or PD/AG as determined by a semi-structured diagnostic assessment (ADIS-5). Based on referrals to the Principal Investigator's ongoing CDA study, it is expected that at least 45% of the recruited Veterans will have served in OEF/OIF and $\geq 50\%$ will be representative of minority groups.

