17. *SAFE-TBT*. The SAFE-TBI was designed to identify the level of evidence for exposure to mild TBI (McAllister et al., 2016). The SAFE-TBI includes a definition of mild TBI as well as three multi-part screening questions, regarding: 1) exposed to, screened for, or put on restricted duty due to any head or brain injury from six examples (e.g., blast or explosion); 2) associated symptoms that occurred immediately after the head or brain injury (e.g., duration of loss of consciousness, feeling dazed or confused, amnesia); and 3) memory loss of events just before or after the injury. The SAFE-TBI has demonstrated moderate levels of agreement for inter-rater and test-retest reliabilities (McAllister et al., 2016). In addition, the SAFE-TBI demonstrated reasonable convergent validity with more extensive measures of TBI in a VA sample.
18. *Veterans Short-Form Health Survey (V/SF-36)*. The V/SF-36 is a 36-item measure designed to assess functional health, well being, and quality of life in Veterans, and can be scored to produce two primary subscales for physical health and mental health (Kazis, 2000). The V/SF-36 was adapted from the original SF-36, which has received extensive support in the literature (Ware & Sherbourne, 1992).

Participants will be asked to complete the assessment materials four times throughout the duration of treatment: pre-treatment, mid-treatment (session 6), post-treatment and six-month follow-up. Participants also will complete select measures bi-weekly to monitor treatment progress.

Potential Risks

There is a potential psychological risk of emotional discomfort during the assessment and treatment procedures. Although this reaction is not uncommon in exposure-based treatments of anxiety and depression and typically is brief in its duration, there are several provisions to reduce and/or avoid it in the proposed study. First, the proposed treatments are designed specifically to target the reduction of emotional distress, anxiety, and

avoidance. Second, if a participant expresses a desire to discontinue treatment due to distress and/or a study clinician determines that participation is counter-indicated, all research and treatment procedures will be terminated.

There is a risk of a loss of confidentiality of personal information as a result of participation in this study. There is a risk of being randomly assigned to a treatment condition that is less effective than the other.

ADEQUACY OF PROTECTION AGAINST RISKS

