4. All assessment and treatment providers will be trained and supervised by the Principal Investigator, Co-Investigator, or one of the staff psychologists involved in the study, each of which is a licensed psychologist. At intake, participants identified by clinical interview with suicidal ideation and acute intent will be excluded from the study and immediately offered emergency psychiatric care at the VAMC. All participants will be completing the PHQ-9 biweekly during the active treatment, in addition to completing those measures and several others at the mid-treatment, post-treatment, and 6-month follow-up time points. During each assessment, the PHQ-9 item 9 will be inspected by the treating therapist/assessor for the presence of suicide ideation (≥ 1 on item 9). If identified, the Columbia Suicide Severity Rating Scale (C-SSRS) will be completed in CPRS. If the C-SSRS is positive, the staff will initiate a warm handoff to a provider in PCMH or Mental Health with support of the project team ([name] is a supervisor in Mental Health) to complete a comprehensive suicide risk assessment. If hospitalization is needed, the PCMH/MHC staff will initiate that process. Upon completion of the warm handoff and comprehensive suicide risk assessment, the provider, research staff, and clinical supervisor ([name]) will discuss ongoing plan. If suicidal ideation is present but not intent, the participant will be retained in the study and reassessed for suicide risk by the investigators in one week. In cases of acute suicidal intent, state law requires immediate hospitalization and these guidelines will be followed.
5. Treatment progress will be assessed throughout the active treatment phase through participant interactions with the therapist as well as completion of self-report measures. Participants who do not respond to treatment or do not complete 12 sessions within a maximum of 18 weeks will be offered mental health treatment with an appropriate VAMC provider.
6. All adverse events associated will be reported to CSR&D program officers and relevant IRBs and data monitoring boards.
7. All participants will be informed if significant information is discovered about the treatment or if other more effective treatment interventions are discovered.

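### TBT could be called well tolerated on attendance, discontinuation and satisfaction, because the plan has no by-arm estimate of how many participants worsen or newly report suicidal ideation

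*Combined protocol and SAP*

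**What the plan says.** All references are to the combined protocol and SAP.

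- **Aims (before section B).** The aim reads "Secondary Aim: To examine feasibility and acceptability of TBT". Its hypothesis is that "TBT will be well tolerated by Veterans as demonstrated by improved attendance" (there measured as weeks to complete treatment), with discontinuation and STTS-R satisfaction, all against the DSTs. The design summary adds: "Process variables (satisfaction, attendance, discontinuation rates) also will be recorded".
- **Section D, Feasibility and Acceptability Analyses.** "Measures of feasibility and acceptability are discontinuation proportions (discontinuation y/n), proportion of sessions attended, proportion of homework assignments completed, and patient satisfaction scores" from the STTS-R. The between-arm models cover the same four domains. Reasons for non-compliance and discontinuation get frequency distributions, with no split by arm stated.
- **Section D, Efficacy Measures Analyses.** The arms are compared on mean PCL-5, PDSS, PHQ-9 and STICSA; everything else is exploratory, and no harm endpoint is listed.
- **Section E, Potential Risks.** Emotional discomfort is named as a risk, with the remark that "this reaction is not uncommon in exposure-based treatments of anxiety and depression". Assignment to the less effective condition is also named.
- **Safety provisions.** PHQ-9 item 9 is checked at each assessment, and a score of 1 or more leads to a C-SSRS in the clinical record, CPRS (section D, Safety Measures; section E, Protection against Risk, item 4). "All adverse events associated will be reported to CSR&D program officers", IRBs and monitoring boards (same list, item 6). The Data and Safety Monitoring Plan, item 1, has a rule based on a 25% worsening at two assessments in a row, which leads to an offer of other treatment.

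**The concern.** Well tolerated is a statement about harm as well as about willingness to attend. The evidence set for it contains no harm outcome, and the safety provisions serve individual care and oversight reporting only. Under the stated rule, better attendance, retention and satisfaction would support the conclusion even if more TBT participants deteriorated or developed suicidal ideation.

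The primary analysis does not close the gap. Two arms can have similar mean scores while one has more participants who get worse, offset by larger gains in others. The trial is meant to support using one protocol in place of three established ones, so readers will want to know whether that happened.

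**Working it through.** The documents state no harm rate, harm margin or power for harm, so there is no figure to reproduce. The check has two parts.

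**1. What is tracked, and whether it is compared by arm**

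| Item | Where | Compared by arm? |
|---|---|---|
| Attendance, homework, satisfaction | Feasibility and Acceptability Analyses | Yes; none is a harm measure |
| Discontinuation (yes/no) | Same | Yes; partial harm proxy |
| Reasons for discontinuation | Same | Frequencies only, no arm split stated |
| Mean symptom scores | Efficacy Measures Analyses | Yes, as means |
| PHQ-9 item 9 | Safety Measures; Protection against Risk, item 4 | No |
| C-SSRS (in CPRS) | Same | No |
| 25% worsening rule | Data and Safety Monitoring Plan, item 1 | No |
| Adverse events | Protection against Risk, item 6 | No |

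Discontinuation is an incomplete proxy for two reasons. Under Missing Data, treatment is also stopped when 12 sessions are not finished within 18 weeks, which need not reflect distress. And a participant who worsens but keeps attending is not counted. The PHQ-9 mean includes item 9, but it does not show how many participants moved from 0 to 1 or more.

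**2. What a by-arm table could show**

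Inputs: 306 in total (Sample Size Determination), so 306/2 = 153 per arm at 1:1. Randomization Procedures gives 108 per arm (2 × 108 = 216, which conflicts with 306), so both are shown. Harm rates p of 5% to 20% are **assumptions**.

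With equal rates in the two arms, the 95% CI half-width for the risk difference is 1.96 × √(2p(1−p)/n). For p = 5%, n = 153: 1.96 × √(0.095/153) = 0.049.

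| Assumed rate | 153 per arm | 108 per arm |
|---|---|---|
| 5% | 4.9 points | 5.8 points |
| 10% | 6.7 | 8.0 |
| 15% | 8.0 | 9.5 |
| 20% | 9.0 | 10.7 |

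Power to detect a doubling (two-sided 0.05) is about 38% for 5% to 10% and 69% for 10% to 20% at 153 per arm, and 29% and 54% at 108 per arm.

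For an assumed 12% against 5%, a difference of 7 points (0.07 × 153 = 10.7, about 11 participants):
- 153 per arm: 1.96 × √((0.12×0.88 + 0.05×0.95)/153) = 6.2 points; power about 60%.
- 108 per arm: the same formula gives 7.4 points, wider than the difference itself.

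With no events in an arm, the one-sided 95% upper bound on the rate, 1 − 0.05^(1/n), is 1.9% at 153 and 2.7% at 108.

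These figures assume complete data. For new item 9 responses the denominator is only those with a baseline of 0, so those intervals would be wider.

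**The case against.** **The aim is feasibility and acceptability, and the measures fit it.** This is true, and the hypothesis defines tolerability within its own sentence. The mismatch lies in one phrase. Narrowing the conclusion would therefore be a sufficient cure, and it is offered below.

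**Discontinuation already reflects harm.** In part. Potential Risks ends treatment when a participant wishes to stop because of distress or a clinician judges participation unsuitable. Those exits count in an outcome that is compared by arm, and reasons for stopping are to be described. It would be wrong to say the comparison has no link to harm. It remains mixed with other causes and blind to those who worsen and stay.

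**A reader might infer that all the harm data are already in hand and only a table is missing.** The documents do not support that. Among the items above, only PHQ-9 item 9 and the symptom scales are clearly research data. The C-SSRS is completed in CPRS. Hospitalisation after baseline appears only as a step in care. Adverse events are to be reported, without definition or grading. The 25% rule names no scale: the item containing it gives the DASS, IIRS and STICSA as examples of the biweekly measures, whereas the assessment section of D lists the PHQ-9, PDSS and PCL-5.

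**A reader might also infer that the documents present TBT as the riskier arm.** They do not. Emotional discomfort is described as a risk of the assessment and treatment procedures generally.

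**Conclusion.** The gap is real but limited. The plan allows a well-tolerated conclusion without any by-arm estimate of deterioration, suicidal ideation or adverse events. It concerns a secondary conclusion and leaves the primary efficacy result unaffected.

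By-arm estimates would be informative for deterioration if it is reasonably common, with half-widths of about 5 to 9 points at 153 per arm and 6 to 11 at 108, under assumed rates of 5% to 20%. One might infer that the trial could reliably reveal an excess such as 12% against 5%. That does not follow: power is about 60% at best, and at 108 per arm an observed 7-point difference would have an interval that includes zero. For the same reason, making tolerability conditional on several harm results without a decision rule would not work, because a null result would not show equal safety.

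Precision could be worse still. Potential Risks ends all research procedures when a participant stops for distress. Missing Data generally keeps participants in the study unless consent is withdrawn or there is a safety concern, and does not say how a distress exit is classed. Harm data may be missing for those most affected.

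**What to change.** 1. In Feasibility and Acceptability Analyses, add a descriptive table by arm: counts, risk difference and 95% CI in all randomised participants, with missing data shown by arm. Include (a) PHQ-9 item 9 of 1 or more after a baseline of 0, with those at baseline 0 as the denominator; (b) deterioration on the study-collected PHQ-9, PCL-5 and PDSS, with the definition written down in advance; (c) adverse events reported under Protection against Risk, item 6; and (d) C-SSRS results and hospitalisations, if they can be extracted from CPRS.
2. Before fixing (b), reconcile the assessment section of D with the Data and Safety Monitoring Plan on which scales are given biweekly and which the 25% rule uses.
3. Tabulate reasons for discontinuation by arm.
4. In the secondary hypothesis, either report well tolerated only alongside these estimates, or limit the conclusion to feasibility and acceptability.
5. State that the harm results are estimates, not a powered test, and that a null result does not establish equal safety.
6. Reconcile Potential Risks with Missing Data on whether assessments continue after a distress exit.

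The cost is SAP wording, one table and a small amount of extra extraction for items held in CPRS or in safety reports. The downside for the sponsor is that a tolerability claim becomes harder to make.

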research team members aware of the randomization assignment. Randomization will occur at the participant level. As such, we will take the following steps to minimize contamination between the two arms of the study: 1) only one member of a household will be eligible for enrollment; and 2) other VA providers will be informed of their patients' participation in the study, but will be blinded to the treatment condition. Although some variability is expected due to the varying prevalence rates of PTSD, PD/AG, and MDD in Veterans, recruitment strategies will be adjusted accordingly if any of the three disorder groups is under-represented (e.g., recruit more heavily in PTSD clinic if PTSD is under-represented).

DSTs Control Condition Matching and Assignment

To provide an evidence-based comparison for the TBT condition, DSTs will be used that are matched to the participant's most severe diagnosis, based upon the average of the ADIS interference and distress scores. If the scores are equivalent for two or more diagnoses, participants will be asked to list which diagnosis/symptoms that they find most impairing. DSTs will be included for each of the three targeted diagnoses, including PTSD (CPT for PTSD), PD/AG (CBT for PD/AG), and MDD (CBT for MDD). Each of these DSTs have published manuals for administration and have received extensive support in the literature (Barlow, 2014). Although several DSTs are available for each disorder (e.g., PE for PTSD, applied relaxation for PD/AG, and behavioral activation for MDD), these three DSTs were selected based on their similarities in cognitive-behavioral techniques as well as their robust evidence in the literature. In addition, all three DSTs have been shown to improve comorbid symptomatology and therefore may be a more accurate comparison to TBT as compared to other available DSTs that may have less effect on comorbidity (e.g., applied relaxation for PD/AG) (Nishith et al., 2005; Tsao et al., 2002).

Treatment Training and Fidelity

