Training workshops (3 days each) will be provided for each of the four treatment protocols, consistent with the standard VA rollout for DSTs. Although less time may be needed for the TBT training ([name] et al., 2017), all four workshops will be standardized in duration to control for potential training differences. Established trainers/experts will be recruited to provide each of the trainings. Trainings will be supported by weekly supervision on the four protocols co-led by VA staff psychologists well-versed in the study therapies for the duration of the study, with additional supervision sessions provided as needed. Backup clinical supervision will be provided by [name] (PI).

Consistent with other well-designed treatment outcome studies, all treatment sessions will be audio recorded with 20% of sessions randomly selected for review for treatment integrity and fidelity. These integrity and fidelity reviews will focus on evaluating the match between the treatment manuals and the material covered in session (e.g., treatment components introduced/reviewed, in session exercise, and homework assigned). To evaluate adherence, treatment-specific rating forms will be used to determine if the therapist appropriately covered the content of each session. External experts will be recruited to rate the recordings independently, with feedback provided to the therapists throughout the duration of the study to maintain/improve treatment delivery.

Safety Measures for Suicidal Ideation or Intent

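### The plan names no therapist-level safeguard against contamination, does not say whether therapists deliver both arms, and does not require other-arm content to be scored or reported

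*Combined protocol and SAP*

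**What the plan says.** **Contamination.** Under *Randomization Procedures* the protocol treats contamination as a threat: "we will take the following steps to minimize contamination between the two arms of the study". It lists two steps. The first is that "only one member of a household will be eligible for enrollment". The second keeps other VA providers blind to condition. Neither concerns the study's own therapists or supervisors.

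**Who delivers what.** *Procedures* says only that each participant gets a project therapist. *Randomization Procedures* limits knowledge of the assignment to one therapist/coordinator role and the statistical analyst. *Treatment Training and Fidelity* says "Training workshops (3 days each) will be provided for each of the four treatment protocols", supported by "weekly supervision on the four protocols co-led by VA staff psychologists well-versed in the study therapies". It does not say who attends which workshop, or whether a therapist sees patients in one arm or both.

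**Fidelity.** In the same section, "all treatment sessions will be audio recorded with 20% of sessions randomly selected for review for treatment integrity and fidelity". The reviews "focus on evaluating the match between the treatment manuals and the material covered in session", with components, exercises and homework given as examples. On adherence, "treatment-specific rating forms will be used to determine if the therapist appropriately covered the content of each session". Finally, "External experts will be recruited to rate the recordings independently, with feedback provided to the therapists throughout the duration of the study". No item for other-arm content, no rating of how distinct the two treatments were, and no report by arm is described.

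**Analysis.** *Efficacy Measures Analyses* plans design effects and a sensitivity analysis for therapist clustering. *Missing Data* plans completer and per-protocol comparisons, but does not define protocol adherers or link them to the fidelity ratings.

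**The concern.** The two arms share much of their technique. *DSTs Control Condition Matching and Assignment* says the three DSTs were chosen partly because their cognitive-behavioural techniques are alike. The account of the TBT pilot in *Preliminary Studies* says TBT keeps other CBT techniques as optional modules. Supervision spans all four protocols. Drift of material from one arm into the other is therefore plausible, and a form that asks whether the assigned content was covered need not register material that was added.

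If that happens, the arms receive more similar treatment than intended and the observed difference shrinks towards zero. In a non-inferiority trial with a positive margin, shrinkage can hide a real deficit of the new treatment. The planned analyses would not reveal it: adjusting for therapist clustering changes the standard error but does not measure leakage, and the per-protocol set has no stated connection to what was delivered.

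**Working it through.** **Inputs from the document**
- One-sided alpha 0.006 (*Sample Size Determination*; 0.025/4 = 0.00625, rounded there).
- Margin 0.5 SD in *Sample Size Determination*; margin 0 in *Efficacy Measures Analyses*, where the interval must exclude 0.
- Expected difference 0.3 SD in favour of TBT (*Sample Size Determination*).
- Total 306, so 153 per arm at 1:1; *Randomization Procedures* gives 108 per arm.
- 12 sessions per participant, 20% of sessions rated.

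**Assumptions.** The document gives no leakage rate. Let c be the share of the true between-arm difference removed by leakage, taken as 10%, 20% and 30%. The calculation is for one outcome with SD 1 at post-treatment, without baseline adjustment, clustering or attrition.

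**The plan's own figure.** The plan has no figure for leakage. Its base sample size is 72 per cell. With n = 2(z₀.₉₉₄ + z₀.₈)²/(0.5 + d)² = 2(2.512 + 0.842)²/(0.5 + d)², d = 0.3 favouring TBT gives 36 per arm and d = 0 gives 90, so 72 is not reproduced. Nothing below depends on it.

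**Formula.** With d the true difference (negative if TBT is worse) and m the margin, P(declare non-inferiority) = Φ( [d(1 − c) + m]/√(2/n) − 2.512 ).

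**Margin 0.5, TBT truly 0.5 SD worse.** At n = 153, √(2/153) = 0.1143. For c = 20%: (−0.40 + 0.50)/0.1143 = 0.875; 0.875 − 2.512 = −1.637; Φ = 5.1%.

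| Leakage c | 153 per arm | 108 per arm |
|---|---|---|
| 0 | 0.6% | 0.6% |
| 10% | 1.9% | 1.6% |
| 20% | 5.1% | 3.8% |
| 30% | 11.5% | 7.9% |

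**Margin 0.5, no true difference.** d(1 − c) = 0 for every c, so leakage changes nothing.

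**Margin 0.5, TBT truly 0.3 SD better, 153 per arm.** The chance of success stays above 99.9% up to c = 30%.

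**Margin 0.** The error rate never exceeds 0.6%, because shrinking a deficit towards 0 cannot carry it past 0. With TBT truly 0.3 SD better at 153 per arm, the chance of success is 54% at c = 0, and 44%, 34% and 25% at 10%, 20% and 30%.

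**What the rated sample can carry.** 306 × 12 × 0.20 = 734 recordings if everyone attends every session (216 × 12 × 0.20 = 518 with 108 per arm). Per participant this is 12 × 0.20 = 2.4 rated sessions. If sessions are sampled independently, 0.8¹² = 7% of participants have none. The sample is large enough for rates by arm but too thin to classify individuals.

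**The case against.** Three stronger readings are tempting, and the documents do not support them.

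*A reader might infer that the therapists are trained in both arms' protocols.* The four workshops, the shared supervision and the single therapist/coordinator role make this plausible, but it is not stated. What stands is that therapist allocation is unspecified.

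*A reader might infer that leakage would go unseen.* The section also plans a comparison of manual with session material, which could show an off-manual exercise or homework task as a mismatch. All sessions are recorded, the raters are external and independent, and therapists receive feedback during the study. The rating forms themselves are not in the document, so nobody can say that a contaminated session would score as fully adherent. What stands is narrower: scoring and reporting other-arm content is not required.

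*A reader might infer that leakage favours non-inferiority in general.* It does so only with a positive margin and a TBT that is truly worse. Under the analysis section's margin of 0 it works against the claim. Under the protocol's own expectation that TBT is better, it lowers the chance of success under either margin, though negligibly at 0.5.

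Two further objections stand in full. Cognitive work in a TBT session may be within protocol through the optional modules, so it cannot simply be counted as leakage. Excluding participants from a per-protocol set because of their rated sessions is not sound either: too few sessions are rated per person, and exclusion on therapist behaviour after randomisation can itself bias the comparison.

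**Conclusion.** The concern holds in a limited form. The listed contamination steps do not reach the study therapists, the plan leaves open whether therapists deliver both arms, and the rating forms are described only in terms of covering the assigned content. Under the 0.5 margin, with TBT truly 0.5 SD worse and 153 per arm, assumed leakage of 10% to 30% would raise false non-inferiority from 0.6% to between 1.9% and 11.5% (1.6% to 7.9% at 108 per arm). Under the margin of 0 there is no inflation, only a lower chance of success. Which consequence applies cannot be settled until the two margins are reconciled.

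The leakage shares are assumptions without a basis in the documents, so these figures show sensitivity and do not predict what will happen. The point is a low-cost improvement in the evidence behind the result. It does not show that contamination will occur.

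**What to change.** In *Treatment Training and Fidelity*:
1. State whether therapists are crossed with arm or nested within it, and who attends which workshop.
2. Add to each treatment-specific form a short list of components unique to the other arm. Leave out any technique that TBT permits as an optional module.
3. Have the same external raters score these items on the same 20% of recordings.

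In the analysis plan:
1. Report off-protocol rates by arm beside the non-inferiority result, as arm-level evidence that the treatments differed. Do not use them to exclude individual participants.
2. Reconcile the margin of 0.5 in *Sample Size Determination* with the margin of 0 in *Efficacy Measures Analyses*, so that the direction in which leakage would matter is clear.

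The cost is the form wording and a few more minutes on each of up to about 734 recordings that the raters will hear anyway. No new recordings or raters are needed. Adding the items later would mean rating the recordings a second time.
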